## 13 Trial Interventions

## 13.1 Investigational Medicinal Product(s) (IMP) Description

Fluenz is a live attenuated nasal spray vaccine against influenza, containing three strains of reassortant influenza virus complying with the WHO recommendation (Northern Hemisphere) and EU decision for the annual season for 2025/2026. Products will be used as supplied by the UK Health Security Agency to NHS sites for routine use. The nasal spray is a colourless to pale yellow suspension which may be clear to opalescent, and small white particles may be present. The ovalbumin content of Fluenz is less than 0.024 micrograms per 0.2 ml dose.

## 13.1.1.1 Dosage, scheduling and packaging

Dose of the vaccine is as described above, with 2 doses of 0.1ml administered per nostril by intranasal spray. There will be no additional labelling of these vaccines beyond their licensed packaging.

## 13.1.2 Placebo description

The placebo is authorised solution of 0.9% saline. stored as routine NHS stock at the study site. Authorised saline is any routine NHS stock vial or ampule of 0.9% saline available at trial sites.

## 13.1.3 Blinding of IMPs

As the investigators are unblinded there will be no blinding of IMPs, however specific instructions will be given to sites to ensure the participant's parent/legal guardian are unable to see which of vaccine or placebo is being given to their child. Specific site training will explain how vaccine/placebo should be handled and the positioning of parent/carer and child to avoid unblinding of the parent/carer.

## 13.1.4 Storage of IMP

Vaccine and placebo will be stored in accordance with manufacturers' recommendations with routine NHS stock at trial sites.

All movements of the study vaccines will be documented in accordance with existing standard operating procedure (SOP). Vaccine accountability, storage, shipment and handling will be in accordance with relevant SOPs and forms. To allow for participants to receive the vaccine in a short time period, additional clinic locations may be used. In this instance vaccines will be transported in accordance with local SOP's and approvals as required. No study-specific tracking or documentation of placebo 0.9% saline is required.

#### 13.1.4.1 Fluenz

Store in a refrigerator ( $2^{\circ}C - 8^{\circ}C$ ). Do not freeze. Keep the nasal applicator in the outer carton in order to protect from light. Before use, the vaccine may be taken out of the refrigerator once for a maximum period of 12 hours at a temperature not above 25°C. Stability data indicate that the vaccine components are stable for 12 hours when stored at temperatures from 8°C to 25°C. At the end of this period, Fluenz should be used immediately or discarded. NHS guidelines recommend Fluenz not be kept out of the refrigerator longer than 20 minutes prior to administration.

### 13.1.4.2 Placebo

Storage as per normal storage instructions for the sites routine stock of vials or ampules of 0.9% normal saline.

## 13.1.5 Compliance with Trial Treatment

All vaccinations will be administered by the research team and recorded in the CRF. The study medication will be at no time in the possession of the participant and compliance will not, therefore, be an issue. At the end of the study period the date of administration of LAIV will be recorded in the child's GP medical records.

## 13.1.6 Accountability of the Trial Treatment

Accountability of the IMPs will be conducted in accordance with the IMP Handling Manual and IMP Management Plan.

#### 13.1.7 Concomitant Medication

As set out by the exclusion criteria, volunteers may not enter the study if they have received: any investigational product within 30 days prior to enrolment or if receipt is planned during the study period, or if there is any use of immunosuppressant medication within 6 months prior to enrolment

or if receipt is planned at any time during the study period (except topical steroids and short course of low dose steroids < 14 day). Volunteers will be excluded in case of prior receipt of any other IMP within 12 weeks or 5 half-lives after the last IMP dose (whichever is longer) before the first dose of study treatment.

## 13.2 Other Interventions

There are no additional investigations other than those specified in this protocol.

## 14 Safety Reporting

## 14.1 Safety reporting window

Safety reporting for the trial will commence once the first participant is consented; and will end after the last participant has attended their final study visit for MAAEs and SAEs.

For individual participants the reporting period begins when consent is confirmed, in person, at the V1 visit, and ends after their final study visit.

All adverse events (AEs) that result in a participants' withdrawal from the study will be followed up until a satisfactory resolution occurs, or until a non-study related causality is assigned (if consent is provided).

### 14.2 Adverse Event Definitions

Adverse Event (AE)	Any untoward medical occurrence in a participant to whom a medicinal product has been administered, including occurrences which are not necessarily caused by or related to that product.
Adverse Reaction (AR)	An untoward and unintended response in a participant to an investigational medicinal product which is related to any dose administered to that participant.  The phrase "response to an investigational medicinal product" means that a causal relationship between a trial medication and an AE is at least a reasonable possibility, i.e. the relationship cannot be ruled out.  All cases judged by either the reporting medically qualified professional or the Sponsor as having a reasonable suspected causal relationship to the trial medication qualify as adverse reactions.
Adverse Events of Special Interest (AESI)	Adverse events identified as being of particular relevance to the IMP's.  These will also reported as an SAE, if meeting SAE criteria (e.g. hospitalisation)
Serious Adverse Event (SAE)	A serious adverse event is any untoward medical occurrence that:  Results in death Is life-threatening

	Requires inpatient hospitalisation or prolongation of existing
	hospitalisation
	Results in persistent or significant disability/incapacity
	Other 'important medical events' may also be considered a serious
	adverse event when, based upon appropriate medical judgement, the
	event may jeopardise the participant and may require medical or
	surgical intervention to prevent one of the outcomes listed above.
	NOTE: The term "life-threatening" in the definition of "serious" refers
	to an event in which the participant was at risk of death at the time of
	the event; it does not refer to an event which hypothetically might
	have caused death if it were more severe.
Serious Adverse Reaction (SAR)	An adverse event that is both serious and, in the opinion of the reporting Investigator, believed with reasonable probability to be due to one of the trial treatments, based on the information provided.
	A serious adverse reaction, the nature and severity of which is not consistent with the Reference Safety Information for the medicinal product in question set out:
6	
Suspected Unexpected	
 
In the case of a product with a marketing authorisation, in the
 

Serious Adverse Reaction	approved summary of product characteristics (SmPC) for that
(SUSAR)	product
	In the case of any other investigational medicinal product, in
	the approved investigator's brochure (IB) relating to the trial
	in question

NB: to avoid confusion or misunderstanding of the difference between the terms "serious" and "severe", the following note of clarification is provided: "Severe" is often used to describe intensity of a specific event, which may be of relatively minor medical significance. "Seriousness" is the regulatory definition supplied above.

## 14.3 Assessment results outside of normal parameters as AEs and SAEs

#### 14.3.1 Clinical

Abnormal clinical findings from medical history or examination will be assessed as to their clinical significance throughout the trial. If an abnormal finding is deemed to be clinically significant, the participant will be informed and appropriate medical care arranged with the permission of the participant's parent/legal guardian.

## 14.4 Assessment of severity

The severity of medically attended and serious adverse events will be assessed according to scales based on FDA toxicity grading scales for healthy adult volunteers enrolled in preventive vaccine clinical trials, listed in Table 1 below.

Table 1. Severity grading for local and systemic AEs

GRADE 0	None
GRADE 1	Mild: Transient or mild discomfort (< 48 hours); No interference with activity; No medical intervention/therapy required
GRADE 2	Moderate: Mild to moderate limitation in activity – some assistance may be needed; no or minimal medical intervention/therapy required
GRADE 3	Severe: Marked limitation in activity, some assistance usually required; medical intervention/therapy required.
GRADE 4	Potentially Life-threatening: Requires assessment in A&E or hospitalisation

### 14.5 Assessment of Causality

For every MAAE or SAE, an assessment of the relationship of the event to the administration of the vaccine will be undertaken by the local PI with CI oversight. An interpretation of the causal relationship of the intervention to the AE in question will be made, based on the type of event; the relationship of the event to the time of vaccine administration; and the known biology of the vaccine therapy. Alternative causes of the AE, such as the natural history of pre-existing medical conditions, concomitant therapy, other risk factors and the temporal relationship of the event to vaccination will be considered and investigated. Causality assessment will be assigned by the reporting investigator, immediately. Causality assessment will be recorded on the eCRF.

If a participant experiences a medically attended adverse event considered possibly, probably, or definitely related to the IMP administration, then the investigator or delegated clinician should

arrange a site visit for safety monitoring assessments where clinically indicated. Investigations and assessment should be performed as felt necessary by the investigator.

Table 2. Guidelines for assessing the relationship of vaccine administration to an AE.

0	No relationship	No temporal relationship to study product and Alternate aetiology (clinical state, environmental or other interventions); and Does not follow known pattern of response to study product
1	Unlikely	Unlikely temporal relationship to study product and Alternate aetiology likely (clinical state, environmental or other interventions) and Does not follow known typical or plausible pattern of response to study product.
2	Possible	Reasonable temporal relationship to study product; or Event not readily produced by clinical state, environmental or other interventions; or Similar pattern of response to that seen with other vaccines
3	Probable	Reasonable temporal relationship to study product; and Event not readily produced by clinical state, environment, or other interventions or Known pattern of response seen with other vaccines
4	Definite	Reasonable temporal relationship to study product; and Event not readily produced by clinical state, environment, or other interventions; and Known pattern of response seen with other vaccines

## 14.6 Procedures for Reporting Adverse Events

## 14.6.1 Medically attended AEs

A medically attended AE, is defined as any adverse event for which the participants' parents/legal guardians seeks medical attention for them either at hospital or from primary care. Participants' parents/legal guardians will be asked to record any medically attended AEs on their electronic diary. Medically attended AEs occurring up to 56 days post randomisation, will be directly solicited and reviewed at each study visit.

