### **Objectives and endpoints:**

Outcomes		
Primary		
Incidence of medically attended, physician- diagnosed wheeze or asthma or an illness for which the child was prescribed asthma medication.		
Secondary		
All medically attended adverse events		

**Brief Summary:** This study is a blinded, cross-over, randomised controlled trial of LAIV compared to placebo nasal spray in children aged 12 to 23 months. The primary outcome is medically attended wheeze in the four weeks following vaccination. To reduce the burden on GPs, study outcomes will be assessed by remote data extraction from electronic health records.

[figure not shown]
There will be two in-person study visits and one visit by digital questionnaire. At the first visit, participants will be consented, screened and randomised 1:1 to receive either LAIV or placebo nasal spray. Four weeks later at the second visit, basic safety information will be collected, and the participants will receive either vaccine or placebo (whichever they did not receive at the first visit). The final visit will be four weeks later and will be conducted via digital questionnaire to collect safety information. Recruitment will be enriched for children with a history suggestive of increased risk of wheezing, including a personal history in the child of eczema, bronchiolitis or viral induced wheeze.

**Number of Participants:** A total of 3000 children are expected to be randomised.

Interventions: All participants will receive live attenuated influenza vaccine (LAIV) (Fluenz, AstraZeneca) during the study. This is a live, attenuated, cold adapted influenza vaccine which is delivered as a nasal spray as 0.1ml solution per nostril. Participants will be randomised to either receive this at the first or second study visit. When not receiving LAIV they will receive 0.1ml per nostril of placebo, administered as normal saline via 1ml syringe and nasal atomiser device. Parents will be blinded to allocation.

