#### 8.2 Potential risks

### 8.2.1 Allergic reactions

Allergic reactions from mild to severe may occur in response to any constituent of a medicinal product's preparation. Anaphylaxis or other hypersensitivity disorders are known to occur in between 1/1000 and 1/100 recipients of LAIV.

(https://www.medicines.org.uk/emc/product/3296/smpc#about-medicine)

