## 9 Objectives and Outcome Measures

Objectives	Outcome Measures	Timepoint(s)			
Primary					
To determine the safety and reactogenicity of LAIV in children	Episode of respiratory wheeze requiring medical attention diagnosed by a health practitioner	Day 0 to 28 following vaccination			
	Key secondary				
To assess safety of LAIV	Serious adverse events	Throughout the study			
	All medically attended adverse events	Throughout the study			

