#### 14.8.2 AESIs

There are no AESIs of special interest as wheeze is a primary study outcome and any hospitalisations will be collected as SAEs.

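### A non-serious reaction managed by trial staff at the dosing visit has no stated reporting category, so an unknown share of the 3 to 30 expected hypersensitivity events may go unrecorded

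*Protocol*

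**What the plan says.** **Risk.** Allergic reaction is the only entry under Section 8.2. Section 8.2.1 states: "Anaphylaxis or other hypersensitivity disorders are known to occur in between 1/1000 and 1/100 recipients of LAIV".

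**Exposure.** Section 3 says "A total of 3000 children are expected to be randomised" and "All participants will receive live attenuated influenza vaccine (LAIV) (Fluenz, AstraZeneca) during the study".

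**What is collected.** Section 14.1 says that trial-level safety reporting "will end after the last participant has attended their final study visit for MAAEs and SAEs". The outcomes table in Section 9 lists SAEs and "All medically attended adverse events" as secondary outcomes. Sections 14.4 and 14.5 assess severity and causality for these two classes only.

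**MAAE definition.** Under Section 14.6.1 the parent or guardian "seeks medical attention for them either at hospital or from primary care".

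**AESIs.** Section 14.8.2: "There are no AESIs of special interest as wheeze is a primary study outcome and any hospitalisations will be collected as SAEs". In Appendix A the late vaccine schedule nevertheless has AESIs in its collection row, while the early vaccine schedule does not. Both schedules of the unfunded sub-study (Section 25.4) list them as well.

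**The concern.** An immediate reaction is most likely to be seen by the research staff who have just given the dose. If they assess and manage it on the spot and it is not serious, the parent has not gone to a hospital or GP, and the event is neither an SAE nor an AESI. As written, no rule tells the site to record it.

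Section 14.8.2 justifies having no AESIs by pointing to wheeze as the primary outcome and to hospitalisations as SAEs. Neither reason covers a non-serious allergic reaction, which is the risk that Section 8.2 singles out and quantifies.

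At stake is the completeness of safety data for a vaccine that Section 6 describes as not approved below two years of age, in a trial whose stated objective is safety and reactogenicity. Section 12.4 makes site staff aware of allocation. If recording depends on how each site reads the definition, it could also differ between vaccine and placebo visits.

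**Working it through.** **1. Source of the 3000.** No stated figure is in dispute here, but the number of recipients rests on Section 15.1. With p1 = 0.009, RR = 2 (p2 = 0.018), two-sided alpha 0.05 and 80% power:

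n = [1.960 × √(2 × 0.0135 × 0.9865) + 0.842 × √(0.009 × 0.991 + 0.018 × 0.982)]² / 0.009² = 2580 per condition

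With continuity correction, n' = (n/4) × [1 + √(1 + 4/(n × 0.009))]² = 2798. This reproduces the protocol's 2800, since each child contributes to both conditions. The protocol rounds up to 3000 for attrition.

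**2. Expected hypersensitivity events after LAIV, all severities and timings** (recipients × rate):

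- 3000 × 0.001 = 3
- 3000 × 0.01 = 30
- With 2800 recipients: 2.8 to 28

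The central 95% binomial range at 3000 is 0 to 7 events at the lower rate and 20 to 41 at the upper.

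**3. Possible routes for a non-serious reaction managed by trial staff at dosing.**

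- *SAE (14.2):* life-threatening and other important medical events qualify; a non-serious reaction does not.
- *SAE alerts (14.7):* the three listed routes are solicitation at follow-up, the eDiary and a parent's direct report. Staff observation at dosing is not among them.
- *MAAE (14.6.1):* depends on the parent seeking care.
- *AESI (14.8.2):* none.
- *Diary (12.5.2):* sent 7 and 14 days after each in-person visit; it asks about contact with a healthcare provider since the last visit or entry, not about reactions.
- *Clinical findings (14.3.1):* assessed for significance, the family informed and care arranged; recording is not mentioned.
- *Withdrawal (12.6):* the reason goes in the CRF, but only if the child is withdrawn.
- *Appendix A:* neither schedule has a row for post-dose reactions.

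None of these clearly captures the event.

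**4. Size of the gap.** Let s be the share of hypersensitivity events that are non-serious and handled only by trial staff at the visit. The number without a stated category is s × 3 to s × 30. The documents do not give s, so the values below are assumptions:

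| s | at 1/1000 | at 1/100 |
|---|---|---|
| 10% | 0.3 | 3 |
| 25% | 0.75 | 7.5 |
| 50% | 1.5 | 15 |
| 75% | 2.25 | 22.5 |

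**The case against.** **The definition is ambiguous rather than clearly excluding.** Section 10.1.1 places sites in primary and secondary care, so treatment there could be read as attention at a hospital or from primary care. This stands, and is why the point is put as the absence of a stated category. It does not settle the matter: the wording turns on the parent seeking care, and Section 13.1.4 allows additional clinic locations.

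**Other routes may catch some events.** Section 12.5.4 includes an interim history at follow-up, Section 16.2 refers to adverse events reported by participants in the diary, and Section 14.11 has investigators reviewing safety continuously. These could pick up a reaction, but none instructs staff to record one they saw themselves.

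**Most of the 3 to 30 go unrecorded.** A reader might infer this, but the documents do not support it. The rate includes anaphylaxis, whose serious cases are SAEs, and reactions after the family goes home that lead to a GP or hospital visit, which are MAAEs. Section 11.3 also excludes children with any history of anaphylaxis. There is no split by seriousness, timing or place of care.

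**A child sent on to A&E is lost.** A reader might infer this from Section 14.7.1, which keeps A&E attendances off the routine SAE route. Such an attendance is medical attention at hospital and so remains an MAAE.

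**Importance.** Section 8.3 names lower respiratory outcomes as the main reason for the trial and lists other common reactions, and no hypersensitivity rate is a listed outcome. It would therefore be too strong to say that a planned estimate is biased. What remains is incomplete safety capture.

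**Conclusion.** The gap is in the text. Only SAEs and MAAEs are collected, the MAAE definition depends on parent-sought care, and the reason for having no AESIs does not address the allergic risk in Section 8.2.1. A non-serious reaction managed by trial staff at dosing can go unrecorded by a site that follows the rules exactly.

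About 3 to 30 hypersensitivity events are expected if the Section 8.2.1 rates apply to these children and all 3000 receive LAIV. The share affected is unknown; at an assumed 10% to 75%, about 0.3 to 23 events have no stated category.

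A reader might also infer that wheeze diagnosed by trial staff at the visit should count towards the primary outcome. The documents give no basis for that. Section 12.5.2 ties the endpoint to families' normal use of health care, and Section 9.1 already supplements GP records with diaries and solicited attendances. Adding diagnoses made by staff who know the allocation would bring an unblinded source into the endpoint. This is an inexpensive improvement to safety capture and does not challenge the primary analysis.

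**What to change.** 1. In Section 14.6.1, extend the MAAE definition to any adverse event assessed or treated by trial clinical staff after dosing at a study visit. Record it on the eCRF with time of onset relative to dosing, and include it in the DSMB tables.
2. Reconcile Section 14.8.2 with the two Appendix A schedules, of which only the late vaccine table lists AESIs. State explicitly whether hypersensitivity or anaphylaxis is an AESI.
3. Report wheeze diagnosed by trial staff at the visit separately as a safety event, and do not add it to the primary endpoint.

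The change concerns data capture only and alters no clinical management. It costs some definition wording, one eCRF field per dosing visit and a few extra reports. The main drawback is that these reports come from staff who know the allocation, so comparisons between vaccine and placebo visits should be read with that in mind.

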## 14.7 Reporting Procedures for Serious Adverse Events

Study sites can be alerted to SAEs via three mechanisms:

• Direct solicitation at follow-up visits.

- Participant reports hospital admission in eDiary (uMed will then notify trial site).
- Participant directly reports SAE to uMed via central telephone number or email on study card (uMed will then notify trial site).

Once the site had been notified of an SAE, the site investigator is required to complete the SAE CRF to notify the Chief investigator or delegate. This may require the investigator to contact the participant's parent/legal guardian to gather information regarding the nature of the SAE. If report of the SAE has come via uMed, they will also notify the CI/delegate of its occurrence so they are aware of a pending report.

In order to comply with current regulations on SAE reporting to regulatory authorities, the event will be documented accurately and notification deadlines respected. SAEs will be reported promptly once the local Investigator/study team becomes aware of their occurrence. Copies of all reports will be forwarded for review to the Chief Investigator (as the Sponsor's representative) or delegate within 24 hours of the Investigator being aware of the suspected SAE. The DSMB will be notified of SAEs that are deemed possibly, probably or definitely related to study interventions; the chair of DSMB will be notified immediately (within 24 hours) of the CI/sponsor being aware of their occurrence. SAEs which are related to a respiratory event will also be reported promptly to the DSMB. SAE will not normally be reported immediately to the ethical committee(s) unless there is a clinically important increase in occurrence rate, an unexpected outcome, or a new event that is likely to affect safety of trial participants, at the discretion of the Chief Investigator and/or DSMB. In addition to the expedited reporting above, the Investigator shall include all SAE in the annual Development Safety Update Report (DSUR) report.

